6.3.3 Stroke

A stroke is defined as an acute episode of neurological dysfunction caused by focal or global brain, spinal cord, or retinal vascular injury.

Stroke will be further sub-classified as:

Ischaemic stroke: An acute focal infarction of the brain or retina (and does not include anterior ischaemic optic neuropathy [AION]).

Criteria:

- 1. Rapid onset of a new focal neurological deficit with clinical or imaging evidence of infarction and not attributable to a non-ischaemic etiology (not associated with brain infection, trauma, tumour, seizure, severe metabolic disease, or degenerative neurological disease); or,
- 2. Rapid worsening of an existing focal neurological deficit that is judged by the Investigator to be attributable to a new infarction. Criteria for symptoms attributable to new infarction *may* include symptoms that persist and are judged by the investigator to be attributable to new infarction, imaging evidence of infarction, or no evidence of a non-ischaemic etiology.

TIA: A neurological deficit of sudden onset, resolving completely, attributed to focal brain or retinal ischaemia without evidence of associated acute focal infarction of the brain.

Criteria:

Rapid onset of a focal neurological deficit that is without evidence of acute focal infarction of the brain, and is not attributable to a non-ischaemic etiology (brain infection, trauma, tumour, seizure, severe metabolic disease, or degenerative neurological disease)

Unknown/No imaging performed: If the type of stroke could not be determined by imaging or other means (from lumbar puncture, neurosurgery, or autopsy) but is judged to fulfil the stroke definition above, the stroke will be classified as ischaemic for purposes of the study.

Haemorrhagic stroke: Haemorrhagic stroke is defined as an acute episode of focal or global cerebral or spinal dysfunction caused by a nontraumatic intraparenchymal, intraventricular, or subarachnoid haemorrhage.

Symptomatic haemorrhagic transformation of an ischaemic stroke: Any extravascular blood within an area of known acute/subacute infarction that is judged to be nontraumatic, and responsible for neurologic symptoms. To be considered symptomatic, the haemorrhagic transformation must be judged to be partially responsible for the patient's clinical neurologic presentation (ie, the area of infarction is not adequate to explain the neurologic deficit, or a secondary neurologic deterioration occurred corresponding to the timing of haemorrhagic transformation).

Criteria (must meet both of the following):

- Imaging evidence (by CT scan or MRI) of extravascular blood within the area of infarction.
- 2. Symptoms judged to be related to the haemorrhagic transformation. Scenarios which may be judged as symptomatic:
- (a) Symptoms are out of proportion to what would be expected for the size and location of the infarct at presentation;
- (b) Clinical deterioration, defined by an increase of 4 points or more in the score on the NIHSS or leading to death, occurring after the initial **ischaemic** event, and identified as the result of the haemorrhagic transformation; or
- (c) Mass effect secondary to the haemorrhagic transformation causing symptoms.

Asymptomatic haemorrhagic transformation of an ischaemic stroke: Any extravascular blood within an area of known acute/subacute infarct, judged to be nontraumatic, without any related neurologic symptoms.

Criteria (must meet both of the following)

- 1. Imaging evidence (by CT scan or MRI) of extravascular blood within the area of infarct.
- 2. No symptoms related to the haemorrhagic transformation, or clinical deterioration with less than a 4 point increase in score on the NIHSS judged to be related to the haemorrhagic transformation.

6.4 Safety

The Principal Investigator is responsible for ensuring that all staff involved in the study is familiar with the content of this section. See Section 6.4.5 for details on reporting of serious adverse events that are also endpoints in the study.

6.4.1 Definition of adverse events

An adverse event is the development of an undesirable medical condition or the deterioration of a pre-existing medical condition following or during exposure to a pharmaceutical product, whether or not considered causally related to the product. An undesirable medical condition can be symptoms (eg, nausea, chest pain), signs (eg, tachycardia, enlarged liver) or the abnormal results of an investigation (eg, laboratory findings, electrocardiogram). In clinical studies, an AE can include an undesirable medical condition occurring at any time, including run-in or washout periods, even if no study treatment has been administered.

The term AE is used to include both serious and non-serious AEs.

Any deterioration of the disease targeted in the study and associated symptoms should not be regarded as an adverse event as far as the deterioration can be anticipated (see Section 6.4.3, Disease progression)

6.4.2 Definitions of serious adverse event

A serious adverse event is an AE occurring during any study phase (ie, run-in, treatment, washout, follow-up), that fulfils one or more of the following criteria:

- Results in death
- Is immediately life-threatening
- Requires in-patient hospitalisation or prolongation of existing hospitalisation
- Results in persistent or significant disability/incapacity or substantial disruption of the ability to conduct normal life functions
- Is a congenital abnormality or birth defect
- Is an important medical event that may jeopardise the patient or may require medical intervention to prevent one of the outcomes listed above

For further guidance on the definition of a SAE, see Appendix B to the CSP.

6.4.3 Recording of adverse events

Time period for collection of adverse events

Only non-serious AEs of interest (ie, bleeding events, dyspnoea, renal impairment/increased creatinine, bradyarrhythmia, increased LFTs, gout/uric acid increases, pneumonia, gynecomastia, abnormal uterine bleeding and all malignancies excluding non-melanoma skin cancers) and discontinuations due to adverse events (DAEs) will be collected from time of randomisation throughout the treatment period and including the follow-up period, until the Study Closure Visit.

All SAEs will be recorded from the time of informed consent, with the exception of events defined as disease progression and those described below.

SAEs will be recorded at all visits in patients who prematurely discontinue treatment with study medication. Non-serious AEs of interest and DAEs will be recorded until the Study Closure Visit but no less than 30 days after last dose of study medication.

Follow-up of unresolved adverse events

Any SAEs and non-serious AEs that are unresolved at the patient's last visit in the study are followed up by the investigator for as long as medically indicated, but without further recording in the eCRF. AstraZeneca retains the right to request additional information for any patient with ongoing AE(s)/DAE(s) and SAE(s) at the end of the study, if judged necessary.

Variables

- The following variables will be collected and recorded for each non-serious AE of interest and DAE:
- AE (verbatim)
- The date when the AE started and stopped
- Maximum intensity
- Whether the AE is serious or not
- Investigator causality rating against the study medication (yes or no)
- Action taken with regard to study medication
- Outcome

In addition, the following variables will be collected for SAEs:

- Date AE met criteria for serious AE
- Date Investigator became aware of serious AE
- AE is serious due to
- Date of hospitalisation
- Date of discharge
- Probable cause of death
- Date of death
- Autopsy performed (if performed)
- Autopsy results
- Causality assessment in relation to Study procedure(s)
- Causality assessment in relation to Other medication
- Description of AE

It is important to distinguish between serious and severe AEs. Severity is a measure of intensity whereas seriousness is described below. An AE of severe intensity need not

necessarily be considered serious. For example, nausea that persists for several hours may be considered severe nausea, but not an SAE.

The following definitions for intensity rating are:

- Mild (awareness of sign or symptom, but easily tolerated)
- Moderate (discomfort sufficient to cause interference with normal activities)
- Severe (incapacitating, with inability to perform normal activities)

Causality collection

The Investigator will assess causal relationship between study medication and each AE, and answer 'yes' or 'no' to the question 'Do you consider that there is a reasonable possibility that the event may have been caused by the study medication?'

Causal relationship in cases where the disease under study has deteriorated due to lack of effect will be classified as no reasonable possibility.

For SAEs causal relationship will also be assessed for other medication and study procedures. Note that for SAEs that could be associated with any study procedure the causal relationship is implied as 'yes'.

A guide to the interpretation of the causality question is found in Appendix B to the CSP

Adverse Events based on signs and symptoms

All non-serious AEs of interest and AEs leading to discontinuation (DAEs) spontaneously reported by the patient or reported in response to the open question from the study personnel: 'Have you had any health problems since the previous visit/you were last asked?', or revealed by observation will be collected and recorded in the eCRF. When collecting AEs, the recording of diagnoses is preferred (when possible) to recording a list of signs and symptoms. However, if a diagnosis is known and there are other signs or symptoms that are not generally part of the diagnosis, the diagnosis and each sign or symptom will be recorded separately.

Adverse Events based on examinations and tests

Results from local laboratory testing performed for the routine care of the patient should only be recorded in the patient chart. If there is a suspicion of Hy's Law liver affection (see appendix D) data on liver enzymes should be entered in the e-CRF. In association with a suspected endpoint event, different assessments may have to be undertaken which could include local laboratory assessments, and will be collected in the patient chart and eCRF as appropriate.

The results from protocol-mandated vital signs will be summarised in the Clinical Study Report. Deterioration as compared to baseline in investigator-initiated assessment of

laboratory values and protocol-mandated vital signs should, therefore, only be reported as AEs if they fulfil any of the SAE criteria or are the reason for discontinuation of treatment with the study medication.

If a non-serious AE of interest, DAE or SAE is detected through deterioration in a laboratory value/vital sign and is associated with clinical signs and symptoms, the sign or symptom will be reported and the associated laboratory result/vital sign will be considered as additional information. Wherever possible the reporting investigator uses the clinical, rather than the laboratory term (eg. renal failure versus increasing creatinine). In the absence of clinical signs or symptoms, clinically relevant deteriorations in non-mandated parameters should be reported as non-serious AEs and SAEs.

NB. Cases where a patient shows an aspartate aminotransferase (AST) or alanine aminotransferase (ALT) $\ge 3x$ ULN **or** total bilirubin $\ge 2x$ ULN may need to be reported as SAEs, please refer to Appendix D to the Clinical Study Protocol 'Actions required in cases of combined increase of Aminotransferase and Total Bilirubin – Hy's Law', for further instructions.

Disease progression

Disease progression can be considered as a worsening of a patient's condition attributable to the disease for which the investigational product is being studied. It may be an increase in the severity of the disease under study and/or increases in the symptoms of the disease. The development of following cerebrovascular events should be considered as disease progression and not an AE. Events, which are unequivocally due to disease progression, should not be reported as an AE/SAE during the study.

- Worsening of stroke signs and symptoms or development of new symptoms consistent with deficits in the original territory of the acute ischaemic infarct. If the event qualifies for new stroke it should be reported as an endpoint.
- New strokes will be reported as endpoints and should not be reported as AE/SAEs (See Section 6.4.5).

6.4.4 Reporting of serious adverse events

All SAEs have to be reported, whether or not considered causally related to the study medication, or to the study procedure(s). All SAEs will be recorded in the CRF.

If any SAE occurs during the course of the study, then investigators or other site personnel inform appropriate AstraZeneca representatives immediately, or **no later than 24 hours** of when he or she becomes aware of it.

The designated AstraZeneca representative works with the investigator to ensure that all the necessary information is provided to the AstraZeneca Patient Safety data entry site within one calendar day of initial receipt for fatal and life threatening events and within five calendar days of initial receipt for all other SAEs.

For fatal or life-threatening adverse events where important or relevant information is missing, active follow-up is undertaken immediately. Investigators or other site personnel inform AstraZeneca representatives of any follow-up information on a previously reported SAE immediately, or **no later than 24 hours** of when he or she becomes aware of it.

Once the Investigators or other site personnel indicate an AE is serious in the WBDC system, an automated email alert is sent to the designated AstraZeneca representative.

If the WBDC system is not available, then the Investigator or other study site personnel reports a SAE to the appropriate AstraZeneca representative by telephone.

The AstraZeneca representative will advise the Investigator/study site personnel how to proceed.

6.4.4.1 Reporting Procedure of Serious Adverse Events using Web-based Data Capture (WBDC) System

The investigators and other site personnel will access WBDC system and report SAE information by entering it into the relevant eCRF module. Upon entry of the SAE information, an automated email alert will be sent to the designated AstraZeneca representative. If the system is unavailable, the investigator(s) should take other appropriate measures to provide the SAE report to the AstraZeneca representative immediately, recognising that the same reporting time frames still apply. The investigators are responsible for completing the eCRF as soon as the system becomes available again.

If initial or the subsequent reports are made by means other than WBDC, necessary information on any SAEs should finally be entered into eCRF via WBDC system by the investigators.

6.4.5 Reporting of serious adverse events that are also endpoints in the study

The following endpoints in the study, although qualifying as SAEs, will only be reported as endpoints:

- Stroke
- MI
- Death

These endpoints will not be reported to health authorities as SAEs to avoid unnecessary unblinding of efficacy endpoints that are also SAEs. In addition, unstable angina and TIAs will also be sent for adjudication to ensure that they are not MI or stroke. If the event of unstable angina or TIA is not confirmed to be an MI or stroke, and it meets SAE criteria, then the event will be reported as an SAE. All other events when meeting SAE criteria will be reported as SAEs, with the exception of procedure related bleeding if expected for the procedure and those events due to underlying disease progression. If it is determined by the

CEC that any of the above events do not meet endpoint criteria, the events if meeting serious criteria will be captured as SAEs and reported to the health authorities as appropriate.

6.4.6 Bleeding assessments

For all bleeding events that are unexpected or of unanticipated quantity, the investigator will complete information on the eCRF specific to that bleeding event. In addition, for all reported bleeding events (excluding those which are self-limited and do not prompt medical evaluation or intervention) relevant information will be compiled and sent to the CEC for adjudication. Additionally, bleeding events will be reported as SAEs if serious criteria are met unless they qualify as endpoints in the study (haemorrhagic stroke and fatal bleeding).

The CEC will adjudicate and evaluate bleeding events (excluding minimal) according to the PLATO bleeding definitions. Programmed algorithms based on data elements collected on the eCRFs will provide TIMI and Bleeding Academic Research Consortium (BARC) classifications ((Mehran 2011).).

6.4.6.1 PLATO definitions of bleeding events

Bleeding events will be classified as shown below:

For patients experiencing a bleeding event that fulfils criteria in more than one category, the bleed will be assigned to the most severe category. The PLATO bleeding definition classification is a modification of the CURE definitions (Yusuf 2001).

Major bleed – fatal/life-threatening

Any one of the following:

- Fatal
- Intracranial
- Intrapericardial bleed with cardiac tamponade
- Hypovolaemic shock or severe hypotension due to bleeding and requiring pressors or surgery
- Clinically overt or apparent bleeding associated with a decrease in Hb of more than 50 g/L^a (3.1 mmol/L^b; 0.775 mmol/L^c)^d

^a Reference range 130 to 180 g/L (males); 120 to 160 g/L (females)

^b Reference range Hb tetramer 8.1 to 11.2 mmol/L (males); 7.4 to 9.9 mmol/L (females)

^c Reference range Hb monomer 2.02 to 2.80 mmol/L (males); 1.85 to 2.47 mmol/L (females)

^d To account for transfusions, Hb measurements will be adjusted for any PRBCs or whole blood given between 2 blood measurements. A transfusion of one unit of blood will be assumed to result in an increase of 10 g/L^a;

 Transfusion of 4 or more units (whole blood or packed red blood cells [PRBCs]) for bleeding.

Major bleed - other

Any one of the following:

- Significantly disabling (eg. intraocular with permanent vision loss)
- Clinically overt or apparent bleeding associated with a decrease in Hb of 30 g/L^a (1.9 mmol/L^b; 0.465 mmol/L^c)^d to 50 g/L^a (3.1 mmol/L^b; 0.775 mmol/L^c)^d
- Transfusion of 2-3 units (whole blood or PRBCs) for bleeding.

Minor bleed

• Requires medical intervention to stop or treat bleeding (eg. epistaxis requiring visit to medical facility for packing).

Minimal bleed

All others (eg. bruising, bleeding gums, oozing from injection sites, etc) not requiring intervention or treatment.

All blood product transfusions during the study will be recorded in the eCRF using both units and volumes of fluid. Bleeding event data will contain all elements needed to classify by TIMI and BARC criteria.

6.4.6.2 BARC definitions of bleeding events

In this study bleeding events will also be classified according to the BARC definitions as shown below. For patients experiencing a bleeding event that fulfils criteria in more than one category, the bleed will be assigned to the most severe category.

Type 0: No bleeding

Type 1: Bleeding that is not actionable and does not cause the patient to seek unscheduled performance of studies, hospitalisation, or treatment by a healthcare professional; may include episodes leading to self-discontinuation of medical therapy by the patient without consulting a healthcare professional

Type 2: Any overt, actionable sign of haemorrhage (eg. more bleeding than would be expected for a clinical circumstance, including bleeding found by imaging alone) that does not

 $^{0.62 \}text{ mmol/L}^b$; 0.155 mmol/L^c in Hb. Therefore, to calculate the true change in Hb if there has been an intervening transfusion between 2 blood measurements, the following calculations should be performed: Δ Hb = [baseline Hb – post transfusion Hb] + [number of transfused units x conversion factor in Hb^e].
^e Conversion factor = 10 g/L^a ; 0.62 mmol/L^b ; 0.155 mmol/L^c

fit the criteria for type 3, 4, or 5 but does meet at least one of the following criteria: (1) requiring nonsurgical, medical intervention by a healthcare professional, (2) leading to hospitalisation or increased level of care, or (3) prompting evaluation

Type 3

Type 3a:

- Overt bleeding plus haemoglobin drop of 3 to <5 g/dL^a (provided haemoglobin drop is related to bleed)
- Any transfusion with overt bleeding

Type 3b:

- Overt bleeding plus haemoglobin drop ≥5 g/dL^a (provided haemoglobin drop is related to bleed)
- Cardiac tamponade
- Bleeding requiring surgical intervention for control (excluding dental/nasal/skin/haemorrhoid)
- Bleeding requiring intravenous vasoactive agents

Type 3c:

- Intracranial haemorrhage (does not include microbleeds or haemorrhagic transformation, does include intraspinal)
- Subcategories confirmed by autopsy or imaging or lumbar puncture
- Intraocular bleed compromising vision

Type 4: CABG-related bleeding^b

- Perioperative intracranial bleeding within 48 h

 Reoperation after closure of sternotomy for the purpose of controlling bleeding

^a Corrected for transfusion (1 U packed red blood cells or 1 U whole blood=1 g/dL hemoglobin).

^b CABG indicates coronary artery bypass graft. Platelet transfusions should be recorded and reported but are not included in these definitions until further information is obtained about the relationship to outcomes. If a CABG-related bleed is not adjudicated as at least a type 3 severity event, it will be classified as not a bleeding event. If a bleeding event occurs with a clear temporal relationship to CABG (ie, within a 48-h time frame) but does not meet type 4 severity criteria, it will be classified as not a bleeding event.

- Transfusion of ≥5U whole blood or packed red blood cells within a 48-h period^c
- Chest tube output $\geq 2L$ within a 24-h period

Type 5: Fatal bleeding

Type 5a:

 Probable fatal bleeding; no autopsy or imaging confirmation but clinically suspicious

Type 5b:

 Definite fatal bleeding; overt bleeding or autopsy or imaging confirmation.

6.4.6.3 Bleeding associated with procedures

Bleeding associated with procedures should **only** be reported as both a bleeding event and an AE/SAE if it exceeds what can be expected for the procedure.

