5.6.5 Surgery

Ticagrelor should be discontinued at least 5 days prior to any surgery. In particular, cardiac surgery and non-cardiac surgery with potential for major bleeding should be performed at least 5 days after stopping study medication. There is a trade-off between stopping study medication too early and risking thrombotic events versus continuing treatment too close to surgery and risking haemorrhage. Thus, it is also recommended that study medication not be discontinued for significantly longer than 5 days so as to minimize the risk of thrombotic complications while off study medication.

Other medication, which is considered necessary for the patient's safety and well being, may be given at the discretion of the investigator and recorded in the appropriate sections of the eCRF.

After surgery, study medications should be restarted when the risk of bleeding is deemed low in the judgment of the investigator, and the investigator should record all peri-procedural bleeding events.

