5.6.6 Other surgery and invasive procedures

For other surgery or other invasive procedures such as coronary angiography or PCI, study medication may be continued or interrupted temporarily at the discretion of the investigator. As with all other surgeries, investigators should collect and record all peri-procedural bleeding events.

After the surgery or procedure, study medications should be restarted (if interrupted) as soon as possible.

Other medication, which is considered necessary for the patient's safety and well being, may be given at the discretion of the investigator and recorded in the appropriate sections of the eCRF.

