6.2.3 Protocol procedures

Patients will have routine visits and procedures as outlined in Section 3.1. Any new suspected endpoint events, non-serious AEs of interest, DAEs, SAEs, and current medications will be recorded in the eCRF. It will be the responsibility of the Investigator to obtain all necessary source documents including medical records from institutions where a hospitalisation may have occurred.

If the patient experiences a suspected clinical efficacy endpoint event or a bleeding event, the following actions should be taken whenever possible and in accordance with current guidelines and local practice standards:

Symptoms of cardiac ischaemia (ie, potentially representing unstable angina or MI):

- Cardiac biomarkers of necrosis (troponin and/or CK-MB) should be collected serially and measured by local labs according to local standards for at least 24 hours.
- A standard 12-lead ECG should be obtained during or as soon as possible after the episode of ischaemia and serially according to local standards until resolution of symptoms.

Coronary Revascularisation (ie, PCI or Coronary Artery Bypass Graft [CABG]):

- Cardiac biomarkers of necrosis (troponin and/or CK-MB) should be measured locally immediately before the procedure and serially (every 8 hours x 3 or until hospital discharge) after the procedure.
- A standard 12-lead ECG should be obtained before the procedure, immediately post-procedure, and, if possible, in the morning following the procedure.
- For patients undergoing major surgery, all banked blood products administered (ie, the number of packed red blood cell or whole blood transfusions [units transfused and volume in mL], fresh frozen plasma [volume in mL], platelets [units transfused and volume in mL] and cryoprecipitate [volume in mL]) and those undergoing CABG, the chest tube output in the first 24 hours should be noted.

Focal neurological symptoms (ie, potentially representing stroke or transient ischaemic attack):

- Complete neurological exam
- Brain imaging (CT scan or MRI)

Bleeding (either unexpected or of unanticipated quantity):

- Record last stable haemoglobin before start of bleeding (or haematocrit if haemoglobin unavailable). Haemoglobin (or haematocrit if haemoglobin unavailable) should be measured locally serially until resolution of the bleeding.
- Record the date, time and number of all banked blood products administered.

Patient health related quality of life

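### Section 6.4.6 opens the bleeding form only for unexpected or unanticipated bleeding, so procedural bleeds that meet PLATO major criteria may go unreferred, depending on the site

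*Protocol*

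**What the plan says.** Section 5.6.5 (Surgery) says that after an operation "the investigator should record all peri-procedural bleeding events". Section 5.6.6 (Other surgery and invasive procedures) repeats the instruction: "As with all other surgeries, investigators should collect and record all peri-procedural bleeding events". Neither sets a threshold.

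Section 6.4.6 (Bleeding assessments) governs the form and the referral. Its entry condition is narrower: "For all bleeding events that are unexpected or of unanticipated quantity, the investigator will complete information on the eCRF specific to that bleeding event". Information is then compiled and sent to the CEC "for all reported bleeding events (excluding those which are self-limited and do not prompt medical evaluation or intervention").

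Section 6.2.3 (Protocol procedures) attaches the same condition to serial haemoglobin measurement and to the recording of blood products for a bleed, under the label "Bleeding (either unexpected or of unanticipated quantity").

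Section 6.4.6.3 says that a procedural bleed is only to "be reported as both a bleeding event and an AE/SAE if it exceeds what can be expected for the procedure".

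Section 6.4.6.1 gives the PLATO definitions. A bleed is major (other) with a haemoglobin fall of 30 to 50 g/L or a transfusion of 2-3 units. It is major (fatal/life-threatening) with a fall of more than 50 g/L or 4 or more units, among other criteria. Nothing there exempts bleeding that was expected or procedural.

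Sections 2.3 and 12.2.2 list time to first PLATO major bleeding event first among the safety variables.

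**The concern.** The endpoint is defined by objective findings, but entry to the process that establishes it depends on whether the site thought the bleeding was expected. The protocol gives no criterion for that judgement. Across approximately 1000 sites, two patients with the same haemoglobin fall after the same operation could be handled differently: one entered and adjudicated, the other not.

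At stake is the completeness and consistency of the leading safety variable. The secondary classifications are exposed too. Section 6.4.6 derives TIMI and BARC classes by algorithm from eCRF data, and BARC type 4 (Section 6.4.6.2) is CABG-related bleeding. If the bleeding page is never opened, the data elements for those classes may be missing as well.

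**Working it through.** No figure in the protocol can be reproduced here, and no arithmetic decides the point. The check sets the rules side by side and follows a case through them.

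| Section | Subject | Expectation test? |
|---|---|---|
| 5.6.5, 5.6.6 | Recording of peri-procedural bleeding | No: all of it |
| 6.3 | Reporting of suspected endpoints | No: all of them, with safety endpoints to be identified in a similar way |
| 6.2.3 | Haemoglobin and blood-product work-up of a bleed | Yes |
| 6.4.6 | Opening the bleeding page | Yes |
| 6.4.6 | Referral to the CEC | Indirectly: only reported bleeds go forward |
| 6.4.6.3 | Reporting of procedural bleeding | Yes, but scope unclear |
| 6.4.5 | SAE reporting of procedural bleeding | Yes, for SAE reporting only |
| 6.4.6.1 | PLATO definitions | No |

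**Case A: operation, 2 units transfused for bleeding, site regards this as usual.**
1. By Section 6.4.6.1 this is a PLATO major bleed (2-3 units).
2. By Section 5.6.5 it is to be recorded.
3. By Section 6.4.6 the bleeding page is not required, because the bleed was neither unexpected nor larger than anticipated.
4. Referral covers reported bleeds. Whether a bleed recorded under 5.6.5 but not entered on the bleeding page counts as reported is not stated.
5. The transfusion itself is in the eCRF, since Section 6.4.6.1 has all blood product transfusions recorded. No text turns that record into a referral.

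**Case B: operation, haemoglobin falls by 30 to 50 g/L, no transfusion, site regards this as usual.**
Steps 1 to 4 are the same, with the haemoglobin criterion in place of the transfusion criterion. Step 5 drops out, because there is no transfusion record. The serial haemoglobin work-up in Section 6.2.3 carries the same expectation condition.

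**The two readings of Section 6.4.6.3.**
- *Reading 1:* an expected procedural bleed is neither a bleeding event nor an AE/SAE. This contradicts 5.6.5 and 5.6.6.
- *Reading 2:* an expected procedural bleed is a bleeding event but is not also an AE/SAE. This agrees with 5.6.5, 5.6.6 and 6.4.5. It still leaves the entry condition in 6.4.6, which concerns the bleeding page itself.

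On either reading, referral in cases A and B is not assured by the text.

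**Do such bleeds fall within the analysis?** They can. Section 5.6.6 allows study medication to continue through procedures such as PCI. Section 12.1.2 censors safety data 7 days after the last dose. If medication was stopped for good 5 days before surgery (the minimum in Section 5.6.5), 7 - 5 = 2 days of the window remain. If it was restarted, the last dose is later and the whole interruption lies inside the window.

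**The case against.** The best defence starts with Section 6.4.6.3. Its natural sense may be reading 2, a limit on double reporting, and on that sense it does not conflict with 5.6.5 and 5.6.6. This stands: that section alone does not prove a contradiction. The finding rests on the entry condition in 6.4.6, which reading 2 does not remove.

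The second defence is that other text pulls such bleeds in. Section 6.3 has sites report every suspected endpoint, including doubtful ones, and treats safety endpoints similarly. Section 6.4.3 lists bleeding among the AEs of interest. Section 5.10 has the CEC adjudicate all primary efficacy and safety endpoints. The referral sentence in 6.4.6 excludes only self-limited bleeds that prompt no evaluation or intervention, which a transfused bleed is not. The CEC charter, which is not at hand, may say more. A reader might infer from 6.4.6 that an expected procedural bleed never reaches the CEC; for these reasons the documents do not support that. But these are partial routes. Section 6.4.6.3 takes expected procedural bleeds out of AE reporting on either reading, and the general rule in 6.3 conflicts with the specific condition in 6.4.6 without any statement of which prevails.

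Third, a reader might infer that the filter hides harm because procedural bleeding is where the drug's excess would show. The protocol does not support this. Section 1.4 reports that in PLATO, against clopidogrel, total major bleeding did not differ, while non-procedural major bleeding was higher with ticagrelor (3.1% vs 2.3%, HR 1.31). Sites here are also blinded, so the judgement of what is expected is made without knowledge of treatment.

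Finally, fatal bleeds and haemorrhagic strokes reach the CEC as death or stroke endpoints regardless. The exposed categories are mainly those defined by haemoglobin fall and transfusion.

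**Conclusion.** The concern holds as a defect of ascertainment. The protocol asks for all peri-procedural bleeding in one place, conditions the bleeding form on site expectation in another, and does not say which governs. As a result, a procedural bleed that meets the PLATO major definition may not be referred, depending on how the site reads the text and what it regards as expected. Capture of time to first PLATO major bleed is therefore incomplete and site-dependent.

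The size cannot be given. The protocol states no procedure rate and no procedural bleeding rate for this population, so any share of the endpoint said to be lost would rest on assumed inputs. Nor would every procedural major bleed be lost, only those that a site calls expected and does not report by another route. No direction of bias is shown.

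The conclusion rests on the protocol text alone and assumes that the CEC charter and eCRF instructions do not already override the condition in Section 6.4.6. If they do, the protocol should still be aligned with them.

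**What to change.** Reconcile Sections 5.6.5, 5.6.6, 6.2.3, 6.4.6 and 6.4.6.3:

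- In 6.4.6 and 6.4.6.3, state that every procedural bleed that could meet a PLATO minor or major criterion is entered on the bleeding page and sent to the CEC, whether or not it was expected.
- In 6.4.6.3, confine the expectation test to AE/SAE reporting, in line with 6.4.5.
- In 6.2.3, extend the haemoglobin and blood-product recording to the same bleeds, so that the CEC has what it needs to classify them.
- In 5.6.5 and 5.6.6, point to the bleeding page as the place of recording.
- Add a flag for procedural status to the bleeding page, so that procedural and other bleeds can be told apart.

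The cost is a wording amendment, one eCRF field with its instructions, and a modest number of extra forms and adjudications. Some of the data are already collected: transfusions for all patients, blood products at major surgery, and chest tube output after CABG.
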